1. GENERAL STATISTICAL PLAN

The data analysis plan *a priori* defines a primary intent-to-treat (ITT) population, a set of secondary evaluation populations, a primary outcome measure, a set of secondary outcome measures, a single primary evaluation time point, a secondary evaluation time point, a primary statistical analysis methodology, a criterion for statistical significance, and guidance for interpretation of results.

The **primary ITT population** is defined as all participants who complete a training set-up visit. Note that this includes all randomized participants except those who drop/withdraw post-randomization and pre-setup visit.

The **primary outcome measure**, per determination of an independent external review committee comprised of experts in the diagnosis and evaluation of the trial target population (i.e., individuals with hemispatial neglect following acquired brain injury), is the Posner cueing task; a spatial attention measure that captures the visual *Field Bias* score (average reaction time to Left trials – average reaction time to Right trials), as reported here:

Rengachary, J., d'Avossa, G., Sapir, A., Shulman, G. L., & Corbetta, M. (2009). Is the posner reaction time test more accurate than clinical tests in detecting left neglect in acute and chronic stroke?. *Archives of physical medicine and rehabilitation*, 90(12), 2081-2088.

To capture a valid assessment of participants' performance in the Posner cueing task (*Field Bias* score) independent of criterion shifts or speed-accuracy trade-offs [Lange-Malecki and Treue, 2012; Spence et al., 2001; Teufel et al., 2010], we will employ an inverse efficiency scoring approach (IES; Townsend and Ashby, 1983) to account for potential differences in accuracy across Left and Right trial types (e.g., Valid and Invalidly cued trials). Mean reaction times (RTs) will be divided by the proportion of correct trials responded to in each specific condition.

The **secondary outcome measures** will evaluate training exercise-based progress, as well as performance in several measures identified by domain, including: spatial attention, spatial cognition, cognitive performance, functional ability, quality of life, and quality of sleep.

Spatial Cognition

- Greyscales Task (raw scores)
- Posner Cueing Task (raw scores)
- Spatial Working Memory Task (raw scores)

Cognitive Performance

- DKEFS Verbal Fluency Letter Fluency (raw scores)
- DKEFS Verbal Fluency Category Fluency total (raw score)
- DKEFS Verbal Fluency Category Switching total (raw score)
- DKEFS Verbal Fluency Category Switching accuracy total (raw score)
- WAIS-IV Digit Span total (sum of forward, backward, sequencing raw scores)
- WAIS-IV Digit Span Forward total (raw scores)
- WAIS-IV Digit Span Backward total (raw scores)

- WAIS-IV Digit Span Sequencing total (raw scores)
- Continuous Performance Task (raw scores)

Functional Ability

- Catherine Bergego Scale total (raw score)
- Barthel Index total (raw score)

Quality of Life

- SF-12 Physical Composite Score
- SF-12 Mental Composite Score

Quality of Sleep

- Pittsburgh Sleep Quality Index total (sum of component scores)
- Pittsburgh Sleep Quality Index Sleep Efficiency (raw score)

The **primary analysis time point** is V2, the post-training assessment. The **secondary analysis time point** is V3, the follow-up assessment.

The **primary statistical analysis methodology** is a linear mixed-effects model approach. We will first compare treatment and active control groups in the ITT population to determine if any differences in baseline demographic, characterization, outcomes variables, or total program use time remain after the randomization process. Any such factors that show trend level significant differences ($p < 0.1$) will be noted and used as covariates in the linear mixed model analysis. We will examine the data from each outcome measure using a linear mixed model with group and time as fixed factors, site as a random factor, and co-variates as necessary from the baseline analysis. Missing data will be handled with an iterative maximum likelihood procedure to optimally estimate model parameters. The key value for significance will be the group-by-time interaction factor for the model. This modeling will be conducted with a Type I error set at 0.05 for each model.

Secondary, exploratory analysis will test for effects in exercise-based progress as well as by domain (e.g., working memory, attention, processing speed) to determine the unique benefit in each area of attention, cognition and independent function. First, to determine if the treatment effect varies based on participants' clinical severity of neglect (Mesulam total misses) or symptom subtype (e.g., sensory loss vs. intact sensory systems), we will correlate neglect severity (or subtype(s)) with gain scores on composite spatial cognition or executive performance and composite functional performance (as well as individual assessment measures). Additionally, we will measure whether improvements on certain components of the training program (e.g., improvements at inhibiting one's response to target stimuli) are associated with composite attention, executive or functional performance scores (as well as individual assessment measures). This could indicate whether certain patterns of training improvements are related more to improvements in attention, executive or functional performance. These analyses will be evaluated after correcting for multiple comparisons (i.e., Bonferroni).

The **criterion for statistical significance** is $p < 0.05$. Results greater than $p = 0.05$ and less than $p = 0.11$ will be described as trends.

To evaluate the effect of the experimental software treatment program (incorporating TAPAT) on spatial attention) we will conduct the analysis based on the pre-training (baseline) and post-training data.

Finding a significance level of $p < 0.05$ on the primary outcome measure will support the statement that the intervention improves spatial attention in the population.

To evaluate the endurance of effects following completion of the experimental software treatment program (incorporating TAPAT) we will use the same modeling approach based on the pre-training assessment (baseline) and end of study (follow-up visit) assessment data using a mixed-effects model parallel to those used to meet the primary and secondary aims. Finding a significance level of $p < 0.05$ on the primary measure will support the hypothesis that the training drives persistent improvement in spatial attention above and beyond an active control.

To identify specific populations of treatment responders and non-responders) we will conduct exploratory data analyses post-hoc to examine predictors of treatment gain and predictors of lack of treatment gain based on baseline participant demographic, cognitive, and functional measures, as well as on learning rate and plateau performance measures derived over the course of the experimental software treatment program (incorporating TAPAT) use. We will initially employ single regression models to identify variables that predict change in cognitive and functional assessments, and then use generalized linear modeling to explore combinations of predictors of treatment gain or lack of gain.

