2. CALCULATIONS FROM CRFS

The following calculations must be made from CRF data to create the required data tables. These calculations are performed automatically by scripts that operate on the tables from the EDCS and produce processed data in new tables.

- Posner Cueing Task
 1. Reaction Time Difference for Left - Right trails of *Field Bias* (Left Valid and Invalid RT – Right Valid and Invalid RT)
 2. Reaction Time Difference for Invalid trails or *disengagement* effect ((Left Invalid-Valid RT) – (Right Invalid-Valid RT))
 3. Reaction Times, Averaged Across All Trials (Left Invalid RT, Right Invalid RT, Left Valid RT, Right Valid RT)
 4. Accuracy, Averaged Within and Across All Trials (Left Invalid RT, Right Invalid RT, Left Valid RT, Right Valid RT)
- Pittsburgh Sleep Quality Index
 1. PSQI total (sum of the component scores, DURAT + DISTB + LATEN + DAYDYS + HSE + SLPQUAL + MEDS)
PSQI Component Scores
 2. Sleep Efficiency is calculated in a two-step process
Step 1: Calculate Sleep Efficiency
Sleep Efficiency = [Duration of Sleep/(Difference between GNT and GMT)]*100

Step 2: Recode Sleep Efficiency

- i. IF Sleep Efficiency ≥ 85 , THEN set value to 0
- ii. IF Sleep Efficiency < 85 and ≥ 75 , THEN set value to 1
- iii. IF Sleep Efficiency < 75 and ≥ 65 , THEN set value to 2
- iv. IF Sleep Efficiency < 65 , THEN set value to 3
3. Sleep Disturbance value is calculated based on the sum of (Q5b + Q5c + Q5d + Q5e + Q5f + Q5g + Q5h + Q5i + Q5j)
 - i. If sum = 0, Sleep Disturbance = 0
 - ii. If sum ≥ 1 and ≤ 9 , Sleep Disturbance = 1
 - iii. If sum > 9 and ≤ 18 , Sleep Disturbance = 2
 - iv. If sum > 18 , Sleep Disturbance = 3
4. Duration of Sleep value is recoded based on hours of sleep indicated
 - i. IF Q4 ≥ 7 , Duration of Sleep = 0
 - ii. IF Q4 < 7 and ≥ 6 , Duration of Sleep = 1
 - iii. IF Q4 < 6 and ≥ 5 , Duration of Sleep = 2
 - iv. IF Q4 < 5 , Duration of Sleep = 3
5. Sleep Latency value is calculated in a two-step process

Step 1: Recode Q2 into Q2new

 - i. IF Q2 ≥ 0 and ≤ 15 , Q2new = 0
 - ii. IF Q2 > 15 and ≤ 30 , Q2new = 1
 - iii. IF Q2 > 30 and ≤ 60 , Q2new = 2
 - iv. IF Q2 > 60 , Q2new = 3

Step 2: Calculate and Recode

 - v. IF Q5a + Q2new = 0, Sleep Latency = 0
 - vi. IF Q5a + Q2new ≥ 1 and ≤ 2 , Sleep Latency = 1
 - vii. IF Q5a + Q2new ≥ 3 and ≤ 4 , Sleep Latency = 2
 - viii. IF Q5a + Q2new ≥ 5 and ≤ 6 , Sleep Latency = 3
6. Day Dysfunction Due to Sleepiness is calculated and re-coded as follows

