population that completed a V3 or delayed follow up visit (the ITT-FEV3 population). Note that a participant may complete a specific visit but have missing data for a test in which case the participant is in the overall FE population but does not contribute data to the FE population for that visit, e.g., the number of evaluable cases for a specific test on a specific visit may be smaller than the FE population for that visit because of missing data.

- v. *Intent to Treat (ITT) Fully-Trained (FT) population:* This is a secondary analysis population, defined as including all members of the ITT-FE population who complete a target number of training visits (32 visits). Note that the FT populations are strict subsets of the FE populations; a person who completes the target number of training visits but does not complete the evaluation visit is not a member of the FT population.
- vi. *Intent to Treat (ITT) Spatial-Bias (SB) population:* This is a secondary analysis population, defined as including all members of the ITT population who demonstrate a bias in spatial attention that is numerically greater on the ipsilesional side of space on the primary outcome measure (Posner cueing task – field bias).

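### The only Field Bias calculation listed in SAP Section 2 is a reaction-time difference, not the inverse-efficiency score that Section 1 specifies for the primary outcome

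*SAP*

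**What the plan says.** Section 1 (General Statistical Plan) introduces the primary outcome, Field Bias on the Posner cueing task, in its base form: "average reaction time to Left trials – average reaction time to Right trials". It then says that inverse efficiency scoring will be used so that the score does not depend on criterion shifts or on trading speed against accuracy, and gives the formula: "Mean reaction times (RTs) will be divided by the proportion of correct trials responded to in each specific condition". Among the secondary outcomes it lists "Posner Cueing Task (raw scores" in parentheses.

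Section 2 (Calculations from CRFs) opens with "The following calculations must be made from CRF data to create the required data tables" and says that scripts perform these calculations automatically. It has four Posner items:

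- Item 1, named Field Bias: "Left Valid and Invalid RT – Right Valid and Invalid RT".
- Item 2, the disengagement effect, also from RTs only.
- Item 3, mean RTs for the four Left/Right by Valid/Invalid cells.
- Item 4: "Accuracy, Averaged Within and Across All Trials (Left Invalid RT, Right Invalid RT, Left Valid RT, Right Valid RT", so the cells listed under accuracy are labelled as RTs.

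Section 3 (Data not from CRFs) also lists the Posner task.

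Two later statements depend on the score. Section 1 says that p < 0.05 "on the primary outcome measure will support the statement that the intervention improves spatial attention in the population". Under Analysis Populations, the Spatial-Bias (SB) population is defined by a bias "numerically greater on the ipsilesional side of space on the primary outcome measure (Posner cueing task – field bias".

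**The concern.** Section 1 says what the primary score is, and Section 2 says what the scripts must produce. The two do not meet. The score that Section 2 produces under the primary outcome's name has no accuracy term, and the score that Section 1 describes is not among the listed outputs. A programmer who follows Section 2 and passes the table named Field Bias to the mixed model would analyse an RT difference.

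The efficacy statement at V2 and the persistence statement at V3 both rest on this one measure. Section 1 adopts IES because a participant can respond faster by accepting more errors, or can become more accurate without becoming faster. The RT-only score counts the first as improvement and misses the second.

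**Working it through.** The SAP gives no figure to reproduce here: it reports no RTs, accuracies or Valid/Invalid trial shares. The check is therefore a comparison of the two definitions, followed by an illustration. **Every RT, accuracy and weight below is an assumption.**

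**Step 1: the definitions.** With one mean RT and one proportion correct (acc) per side:

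- Section 2, item 1: raw = RT_L − RT_R
- Section 1: IES = RT_L/acc_L − RT_R/acc_R

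If accuracy has the same value *a* in every cell, participant and visit, then IES = raw/*a*. That is a constant rescaling, and it leaves the group-by-time test unchanged. The two scores can lead to different results only where accuracy differs between sides, people or visits.

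**Step 2: one visit** (left 725 ms, right 600 ms at 97%, so 600/0.97 = 618.6).

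| Left accuracy | Raw | IES |
|---|---|---|
| 97% | 125 | 747.4 − 618.6 = 129 (unrounded 128.9) |
| 95% | 125 | 763.2 − 618.6 = 145 |
| 90% | 125 | 805.6 − 618.6 = 187 |
| 80% | 125 | 906.3 − 618.6 = 288 |
| 70% | 125 | 1035.7 − 618.6 = 417 |

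In the 97% case, a 50 ms gain in left RT is 50 ms raw and 50/0.97 = 52 ms IES, which is no practical difference.

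**Step 3: change over time** (right 600 ms at 98% throughout, so 600/0.98 = 612.2).

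- Faster but less accurate: left goes from 800 ms at 90% to 700 ms at 78.75%. Raw improves by 100 ms. IES is 888.9 − 612.2 = 277 ms at both visits, a change of 0.
- More accurate at the same speed: left stays at 800 ms while accuracy goes from 80% to 95%. Raw change is 0. IES goes from 1000 − 612.2 = 388 to 842.1 − 612.2 = 230, a fall of 158 ms.

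**Step 4: sign.** Left 590 ms at 90%, right 600 ms at 98%: raw is −10 ms, and IES is 655.6 − 612.2 = +43 ms. If SB membership is read from the sign, the two scores classify this participant differently.

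**Step 5: combining Valid and Invalid cells.** Section 1 does not state the weights. Assume Left Valid 700 ms at 90%, Left Invalid 900 at 60%, Right Valid 580 at 99%, Right Invalid 640 at 97%. The cell IES values are 777.8, 1500, 585.9 and 659.8.

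- Equal weights: raw 800 − 610 = 190; IES 1138.9 − 622.8 = 516.
- 75% valid: raw 750 − 595 = 155; IES 958.3 − 604.3 = 354.

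The weights move both scores, so the added formula must state them.

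**The case against.** The strongest reply is that Section 1 already settles the matter. It attaches IES to the Field Bias score by name, and a list of intermediate tables does not override an outcome definition. Section 2 says which calculations are required, not that no others will be made; the domain composites, for instance, are derived in Section 4. Items 3 and 4 appear to supply the RT and accuracy that the IES quotient needs, and Section 3 shows that Posner data also exist outside the CRF tables. Item 1 fits the secondary raw Posner score.

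Most of this stands, and it rules out several stronger readings that a reader might infer:

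- *That the primary outcome is undefined, or that the choice between raw and IES is left open.* Section 1 chooses IES.
- *That IES cannot be computed.* Its inputs are available.
- *That the SB population has no defined score.* It refers to the primary outcome measure and so inherits its scoring.
- *That the missing weighting is a defect of equal rank.* Division by cell is the natural reading of Section 1, and the publication cited there for the base score may settle how cells combine; it was not available to check. This is a missing detail.
- *That the RT labels in item 4 show that accuracy is not collected.* They look like a copying slip.

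The reply does not remove the mismatch. Item 1 is labelled neither raw nor secondary, and it carries the primary outcome's name. If it is the secondary score, then Section 2 lists no derivation of the primary score at all, although it spells out the sleep index, a secondary outcome, step by step.

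**Conclusion.** The point holds as a mismatch between definition and derivation: the listed script output named Field Bias is not the primary score that Section 1 prescribes, and the primary score is not listed in Section 2. If that output were analysed as the primary outcome, the protection against speed-accuracy trade-off would be lost.

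The size cannot be determined from the SAP. It is negligible if accuracy is high and equal on both sides. It is material if left accuracy is lower, or changes between visits, particularly if it changes differently in the two arms. The illustrations run from a 4 ms difference to a 100 ms raw gain with no IES gain, but they rest wholly on assumed inputs, and 78.75% was chosen so that the IES change is exactly zero.

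A reader might infer from the larger IES figures that the trial's conclusion would change. The document does not support that: raw and IES milliseconds are different scales, and no effect on the interaction p-value, power or type I error has been shown.

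**What to change.** In Section 2, add the primary variable by name, for example Field Bias (IES, primary): mean RT divided by proportion correct in each of the four Left/Right by Valid/Invalid cells, combined within each side by one weighting fixed before unblinding (equal weights would be one option), then Left minus Right. Relabel item 1 as the secondary raw RT score.

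Two minor clarifications can go in at the same time: correct the cell labels in item 4 to proportion correct, and note in the SB definition that the IES score applies, as its reference to the primary outcome implies.

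The cost is a few lines of SAP text and a script edit, using RT and accuracy data that the plan already covers. No new data are needed.

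### Total program use time accrues after randomisation, yet the p<0.1 screen can make it a covariate in the primary model, in a form the SAP does not state

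*SAP*

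**What the plan says.** The primary methodology paragraph of SAP section 1 (General Statistical Plan) sets up a comparison of the arms in the ITT population, looking for "differences in baseline demographic, characterization, outcomes variables, or total program use time remain after the randomization process". Factors that differ at p<0.1 "will be noted and used as covariates in the linear mixed model analysis". The model has group and time as fixed factors, "site as a random factor, and co-variates as necessary from the baseline analysis", and is fitted to each outcome measure. The deciding test is stated: "The key value for significance will be the group-by-time interaction factor for the model".

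For the primary question, "we will conduct the analysis based on the pre-training (baseline) and post-training data", and p<0.05 "on the primary outcome measure will support the statement that the intervention improves spatial attention in the population". For persistence of effect, "we will use the same modeling approach based on the pre-training assessment (baseline) and end of study (follow-up visit) assessment data", so the same covariate rule carries over to V3.

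The SAP does not define total program use time. It does give the order of events: the ITT population is "all randomized participants except those who drop/withdraw post-randomization and pre-setup visit", so the training set-up visit comes after randomisation. The Analysis Populations section says the same.

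**The concern.** A baseline variable can differ between arms after randomisation only by chance. Program use time is different in kind. It builds up during training, and the assigned program can itself change it, for instance if one program is more engaging or more tiring than the other. A difference in use may therefore be a result of assignment.

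The limiting phrase about covariates coming from the baseline analysis does not exclude use time, because that analysis is the very comparison that names it. Elsewhere the SAP keeps training exposure out of the primary comparison. Completion of 32 training visits defines a secondary population, and learning measures taken during program use belong to post-hoc exploratory work.

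The efficacy statement rests on this model. If use time enters so that it can alter the group-by-time estimate, a real benefit may be hidden or an apparent one created, depending on which arm uses its program more. Because the form of entry is not fixed, the choice could be made after the data are seen.

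**Working it through.** The SAP gives no sample size, use-time difference or correlation for this purpose, so there is no stated figure to reproduce. All numerical inputs below are assumptions, shown over a range.

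**1. Main-effect entry.** Use time is one value per participant, the same at both visits. With baseline and V2 both observed, the group-by-time estimate is the difference between arms in mean change. A term that is constant across the two visits cancels from each participant's change:

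(y₂ + c·use) − (y₁ + c·use) = y₂ − y₁.

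- One simulated data set of 400 participants gave a group-by-time estimate of 0.383 without use time and 0.383 with it as a main effect. With use time by time it was 0.266.
- With about 17% of V2 values missing, depending on use, the three estimates were 0.324, 0.325 and 0.226.
- In repeated trials with 15% and 22% of V2 missing in the two arms because of low use, main-effect entry moved the mean estimate by 0.003–0.004 SD. Rejection under the null was 4.9–5.4%, against 5.1–5.5% without use time.

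**2. By-time entry: size of the bias.** Assume gain has SD 1, use time has SD 1 within arm, the correlation of use with gain is r, and the systematic arm difference in use is d. There is no true effect, and use is a marker of a shared cause of gain: the arm shift in use does not itself produce gain. When use time is selected, the adjusted estimate is the unadjusted one minus about r × D, where D is the observed arm difference in use. So

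bias ≈ −r × E[D × 1(selected)].

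With m per arm, SE(D) = √(2/m), and selection needs |D| > t × SE(D), with t the two-sided 10% critical value. Let z = (t·SE − d)/SE. Ignoring the negligible opposite tail,

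E[D × 1(selected)] = d × P(selected) + SE × φ(z).

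At m = 50, d = 0.5, r = 0.4:
- SE = √(2/50) = 0.200; threshold = 0.332; z = (0.332 − 0.5)/0.200 = −0.84.
- P(selected) = 0.80 and φ(z) = 0.280.
- 0.5 × 0.80 + 0.200 × 0.280 = 0.456, so bias ≈ −0.4 × 0.456 = −0.18 SD.

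The same steps give −0.16 at 30 per arm and −0.19 at 75 per arm.

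**3. By-time entry: error rate and power.** Simulated trials applied the p<0.1 screen, then regressed gain on arm, with use time added when selected. With complete two-visit data this is equivalent to a covariate-by-time term. Columns are 30, 50 and 75 per arm.

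| Setting (d, r, true effect) | 30 | 50 | 75 |
|---|---|---|---|
| 0.5, 0.4, none: use time selected | 60% | 80% | 92% |
| 0.5, 0.4, none: false rejection | about 10% | about 15% | about 24% |
| 0.3, 0.4, none: false rejection | 5.5% | 7.0% | 9.2% |
| 0.3, 0.2, none: false rejection | about 5% | 5–6% | 5–6% |
| d = 0, 0.4, none: false rejection | 4–5% | 4–5% | 4–5% |
| true effect 0.5 SD: power without use time | 48% | 70% | 86% |
| same, treatment arm uses 0.5 SD more, r = 0.4 | 26% | 37% | 50% |
| same, control arm uses 0.5 SD more, r = 0.4 | 72% | 94% | 99% |

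In the last row the higher rejection rate reflects an estimate biased upward by 0.16 to 0.19 SD; it is not a gain in valid power.

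**4. Use time as a mediator.** Assume a direct effect of 0.3, 0.4 per SD of use and a 0.5 SD arm difference in use, so the total effect is 0.3 + 0.4 × 0.5 = 0.5. At 50 per arm the rule with by-time entry gives a mean estimate of 0.32 and power 46%, against 0.50 and 78% unadjusted.

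**The case against.** The strongest reply is that the SAP never writes a covariate-by-time term or a change-score model for the primary analysis. The only interaction it names is group-by-time, and the gain scores it mentions belong to exploratory correlations. Covariates added to such a model would ordinarily be read as main effects, and then the deciding estimate does not move. This stands, and it sets the limit of the point: a reader might infer that the primary analysis is biased as written, but the document does not support that.

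A reader might also infer that the by-time form is biased whenever the arms differ in use. That is too broad. A difference arising by chance causes no average bias, as the d = 0 row shows. The assigned program must systematically change use, and use must be related to gain.

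The larger error rates need a sizeable difference in use together with a fairly strong correlation. With weaker inputs there is little inflation. The null figures also treat use as a marker of a shared cause; if use itself produced gain, a zero total effect would need an exactly offsetting direct effect.

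The definition of use time and the covariate form may be in the protocol, which is not at hand. That does not rescue the SAP's own wording, which places use time among differences left after randomisation.

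Finally, the p<0.1 screen makes the covariate set depend on the data, but it does not by itself inflate the overall error rate. It is a lesser matter.

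**Conclusion.** The rule is wrong as written and should be fixed. A post-randomisation variable is screened as if it were a baseline imbalance and can enter the model that decides efficacy. Under main-effect entry the adjustment is pointless. Under by-time or change-score entry the comparison no longer estimates the intent-to-treat effect.

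For the second form, with 30 to 75 per arm, false rejection ranges from about 5% (0.3 SD, correlation 0.2) to about 10–24% (0.5 SD, correlation 0.4). At the stronger inputs a true effect of 0.5 SD loses roughly half of its power at 30 and 50 per arm, and somewhat less at 75, if the treatment arm uses the program more; it is overstated if the control arm does. These sizes rest wholly on assumed sample sizes, use differences and correlations. They show what the open wording permits and do not predict this trial's result. Confidence is high that use time does not belong in the screen, and only moderate that it would do harm, because the harm depends on a model term that the SAP leaves unstated.

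**What to change.** Remove total program use time from the covariate screen and from all primary and secondary outcome models at V2 and V3. Report it by arm, or use it in a labelled exploratory dose analysis alongside the planned predictor work.

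Replace the p<0.1 screen with a short list of baseline covariates named in advance. Write out the model, stating for each covariate whether it enters as a main effect or also with time. Adjustment for chance baseline imbalance can be kept as a sensitivity analysis.

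The cost is SAP wording only, before unblinding, with no new data or visits. Nothing is lost under the main-effect reading, since use time does not move the complete-data estimate there.

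### The primary mixed model names site as its only random factor and sets no within-participant covariance, so the group-by-time test loses power if fitted as written

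*SAP*

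**What the plan says.** Everything on this point is in section 1 of the SAP (General Statistical Plan).

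- **Model.** Each outcome is analysed with a "linear mixed model with group and time as fixed factors, site as a random factor", plus "co-variates as necessary from the baseline analysis".
- **Key test.** "The key value for significance will be the group-by-time interaction factor for the model". The Type I error is 0.05 for each model.
- **Data in the primary model.** For the effect on spatial attention, "we will conduct the analysis based on the pre-training (baseline) and post-training data". That gives two scores per participant.
- **Follow-up.** Persistence is tested on baseline and V3, "using a mixed-effects model parallel to those used to meet the primary and secondary aims". That again gives two scores per participant.
- **Covariates.** The groups are compared to see "if any differences in baseline demographic, characterization, outcomes variables, or total program use time remain after the randomization process". Factors that differ at p < 0.1 "will be noted and used as covariates in the linear mixed model analysis".
- **Missing data.** "Missing data will be handled with an iterative maximum likelihood procedure to optimally estimate model parameters".

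No section names a participant effect, a repeated-measures covariance or a robust standard error.

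**The concern.** The group-by-time interaction is a comparison of within-participant change. Its precision depends on how strongly a participant's two scores are correlated. A site effect captures only what participants at one site have in common, and it largely cancels from this contrast. With site as the only random term, the model takes a participant's baseline and later scores as independent given site, and computes the standard error (SE) on that basis.

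This test decides the primary claim. The same model serves the V3 persistence claim and every secondary outcome. An SE that is too large means a real effect can be missed. The missing-data statement suffers too: without a link between visits, maximum likelihood cannot use a dropout's baseline score to inform the missing later score.

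**Working it through.** **Inputs.** From the SAP: two visits per model, site as the only random term, group-by-time as the test, level 0.05. The SAP gives no sample size, power, SD or within-participant correlation, so there is no design figure to reproduce. Assumed: a two-sided test, 80% power for a correctly specified model, equal variance s² at both visits, n per arm, complete data, and rho (net of site and covariates) of 0.1, 0.3, 0.5 or 0.7.

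**Step 1: SE ratio.** The variance of a participant's change is 2s²(1 - rho), so the true variance of the group-by-time contrast is 4s²(1 - rho)/n. The site-only model reports about 4s²/n. Reported SE / true SE = 1/sqrt(1 - rho).

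**Step 2: level and power.**
- Actual level = 2 × [1 - Φ(1.96/sqrt(1 - rho))]
- Actual power = Φ(2.80 - 1.96/sqrt(1 - rho)), where 2.80 = 1.96 + 0.84

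| rho (assumed) | SE ratio | Actual level | Power (nominal 80%) |
|---|---|---|---|
| 0.1 | 1.05 | 3.9% | 77% |
| 0.3 | 1.20 | 1.9% | 68% |
| 0.5 | 1.41 | 0.6% | 51% |
| 0.7 | 1.83 | 0.03% | 22% |

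Example at rho = 0.5: 1.96/sqrt(0.5) = 2.77; level 2 × [1 - Φ(2.77)] = 0.6%; power Φ(2.80 - 2.77) = Φ(0.03) = 51%.

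**Step 3: sensitivity.**
- *Unequal variances.* If the SDs at the two visits differ by a factor of 2, the ratio is sqrt(5/(5 - 4 rho)) = 1.04, 1.15, 1.29, 1.51.
- *Other covariates.* A covariate that is constant over time and explains a share R² of the outcome variance shrinks the reported SE but not the true one. In terms of the correlation before covariate adjustment, the ratio is sqrt((1 - R²)/(1 - rho)). With R² = 0.2 assumed, it is 1.07 rather than 1.20 at 0.3 (power 76%, not 68%), and 1.26 rather than 1.41 at 0.5 (power 63%, not 51%). This is why rho in the table must be read as net of covariates.

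**Step 4: simulation** (assumed 40 per arm, 4 sites, site variance 0.1, 300 runs per scenario). At rho = 0.5 the site-only SE averaged 0.311 against an empirical SD of 0.222, with null rejection 1.0% and power 55%. A participant-level analysis gave SE 0.223, null rejection 5.0% and power 81%. At rho = 0.7 the site-only SE was 0.309 against 0.181, with power 25% against 75%.

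**Step 5: the covariate rule.** Baseline outcome variables are among the factors screened at p < 0.1. Suppose an outcome's own baseline is triggered and entered on both of a participant's rows, including the one where it is the response.
- The pooled slope is (1 + rho)/2 and the mean residual variance is s²(1 - rho)(3 + rho)/4. With complete data the estimate is unchanged, and reported SE / true SE = sqrt((3 + rho)/4) = 0.88, 0.91, 0.94, 0.96, which is now too small.
- Null rejection within this branch (about 10% of trials under the null) is 33%, 25%, 18%, 12%. With a correct SE it would still be 23%, 19%, 15%, 11%, because the branch selects trials with a chance baseline imbalance.
- Over all trials the site-only level is 5.3%, 3.5%, 2.1%, 1.3% and power 78%, 69%, 53%, 27%.
- A participant term does not work properly alongside this covariate. The residual covariance becomes -s²((1 - rho)/2)², which is negative, so a random-intercept variance is estimated at zero and the site-only SE returns. With an unstructured covariance, the baseline residual variance tends to zero as the slope tends to 1, and the likelihood is unbounded.

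**The case against.** **The sentence may not be a complete list.** It also omits the interaction term, which the same paragraph makes the key test. The plan calls the method a mixed-effects approach and relies on maximum likelihood for missing data, which has little purpose unless a participant's visits are linked. Many analysts would add a participant effect by custom. This stands as evidence of likely intent. It does not supply the structure: on this reading the covariance behind the primary p-value is still chosen at analysis, although the plan says that it defines its primary methodology in advance. A protocol may say more, but the SAP does not defer to one here. It specifies the model and names one random factor.

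**The size is not known.** This also stands. Both rho and the 80% are assumptions, and triggered covariates reduce the loss.

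**A stronger reading to avoid.** A reader might infer from Step 5 that the plan inflates false positives, so that a positive result would be unsafe. The document does not support that. It would take a second literal reading, in which an outcome serves as covariate for itself; the SAP screens baseline outcome variables but does not say this. Even then, most of the rejection in that branch comes from baseline imbalance that a correct SE would leave in place, and the overall level is at most about 5.3% at the values of rho examined. Outside that branch, with positive rho, the test is conservative.

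**Conclusion.** The point holds as a fault in the stated model: two scores per participant, site as the only random term, and nothing that links the scores. Fitted as written with positive correlation, the SE of the decisive test is too large and the main consequence is lost power. The loss runs from about 3 percentage points at rho = 0.1 to 58 at rho = 0.7 (80% to 77%, and 80% to 22%). Those figures rest on equal variances, complete data, rho net of site and covariates, and a nominal 80% that the SAP does not state. If the sentence is read as incomplete, the fault is an unspecified covariance, and the same change cures it. The own-baseline covariate is a secondary matter that belongs with the covariate rule. This should be fixed before the analysis; confidence is medium, because the harm depends on a literal fit and on an unknown rho.

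**What to change.** 1. For the baseline-V2 and baseline-V3 models, state: fixed effects for group, time and their interaction; a random effect for site; and an unstructured covariance for the two scores of one participant. A participant random intercept nested in site is an acceptable alternative. Name one of the two in advance.
2. As a companion clause to the covariate rule, state that an outcome's own baseline score, being already a response in the model, is not also entered as a covariate when it differs at p < 0.1.

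The cost is two clauses and one extra covariance parameter (random intercept) or two (unstructured), with no new data. In a simulation with 50 per arm assumed, a participant term without the own-baseline covariate gave a level of 4.9% to 5.1% and kept power at 80% for rho from 0.1 to 0.7. The change does not remove the effect of a chance baseline imbalance within a given trial.
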